3.8. Data Display Characteristics

Data displays produced for this study will include data listings, summary tables, and figures. Unless stated otherwise, data listings will be produced for all recorded data. Summary tables will be produced as specified in following sections. Additional data listings will be produced for outcome measures that involve extensive procedures to derive the analyzed outcomes. Figures will be produced when specified in sections to follow. Final delivery of tables, listings, and figures will have numbering in compliance with the ICH E3 guideline. Prior to compilation of the clinical study report, Novella standard TREF, FREF, and LREF reference numbers will be used.

Data listings will simply list the data recorded in the eCRF or derived for each patient. They will be ordered by phase (escalation or expansion), cohort, patient number, and time of assessment. When expedient, additional levels of ordering hierarchy may reflect subsets of assessments within patient. Data listings will not display patient initials.

Summary tables will display summary statistics calculated for each of the dose cohorts or treatment groups, unless described otherwise in following sections. See shell tables for specific formats.

The summary statistics displayed will be a function of the type of data associated with the summarized assessment. For categorical variables, the number and percent of each category within a parameter will be calculated. For continuous variables, the sample size (n), mean, median, and standard deviation, as well as the minimum and maximum values, will be presented. Some continuous variables may also be grouped into categorical levels and evaluated in frequency tables.

4. PATIENT ACCOUNTABILITY

4.1. Patient Characteristics

Patient characteristics will be summarized and listed for the Safety population.

4.1.1. Demography

Demography will include age, race, ethnicity, gender, ECOG performance status, and cancer stage at study entry.

Age will be calculated as (First Dose Date – Birth Date + 1)/365.25, rounded down to the nearest whole number. This corresponds to the typical calculation of age a person would use in conversation.

4.1.2. Height and Body Weight

Height, weight, and AIBW at baseline will be summarized.

4.1.3. Cancer History

Cancer history will summarize: stage of cancer at diagnosis; prior radiation therapy (yes/no); prior cancer systemic therapy (number of regimens), prior cancer-related surgery (yes/no).

Cancer histories will be summarized for the Safety population as the numbers and percentages of patients with histories significant for each of the cancer history elements.

4.1.4. Medical History

Medical history will be coded using Medical Dictionary for Regulatory Activities (MedDRA) (version 18.1 or later), associating lower-level terms with preferred terms and system organ classes by the primary hierarchy. All medical history information will be provided in listings.

4.2. Patient Disposition

A summary of patient disposition will show the total number of patients who were treated and the number of patients treated in each relevant treatment group. The reasons for discontinuation will be summarized by categories included on the End of Study form as listed below, the summary will include the total number and percentage of patients per category and the number of patients and percentage of patients in each relevant treatment group. Percentages of patients will be calculated using all members of the relevant population in the relevant treatment group for the denominator.

End of Study form categories for discontinuation are:

- One year post treatment without PD or subsequent therapy
- Adverse Event
- Disease progression
- Clinical Progression
- Began new anti-cancer therapy
- Study Terminated by Sponsor
- Withdrawal from Study
- Investigator decision

- Lost to follow up
- Death
- Other

End of Treatment information, including reason for discontinuation of IMGN853, will also be summarized.

4.2.1. Protocol Deviations and Population Inclusions

Protocol deviations will be summarized by the categories used in the protocol deviation log as follows:

- Patients who were enrolled into the study even though they did not satisfy all of the entry criteria
- Patients who developed withdrawal criteria during the study but were not withdrawn
- Patients who received the wrong treatment or incorrect dose
- Patients who received an excluded concomitant treatment

A listing of all deviations will also be presented.

5. EFFICACY ANALYSES

Efficacy analyses will use data from the Response-Evaluable population unless otherwise specified. Unless stated otherwise, patients will be analyzed in the following groups: Escalation Schedule A, Escalation Schedule B, EOC Expansion Cohorts, Endometrial Expansion Cohort.

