11. STATISTICAL METHODS

All descriptive statistical analyses will be performed using the most recently released and available SAS statistical software, unless otherwise noted. For categorical variables, the number and percent of each category within a parameter will be presented. For continuous variables, the sample size (n), mean, median, and standard deviation, as well as the minimum and maximum values, will be presented. Missing data will not be imputed unless otherwise stated. There will be a detailed description of patient disposition, patient demographics, and baseline characteristics.

No formal interim analysis is planned for this study. However, a review of safety data and available preliminary PK data will be conducted by the CRC after the MTD or a RP2D for IMGN853 has been determined. Results from this data review could enable selection of dose and dosing schedule for additional studies with IMGN853, before full completion of this study.

A statistical analysis plan (SAP) will fully describe the planned analyses for this trial. All analyses will be performed for any patient that received study drug. All analyses for efficacy will use Cycle 1, Day 1 as the start time.

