11.4. Efficacy

Objective response rate (ORR) - The best OR will be determined by the Investigator for each patient as either CR, PR, SD or relapsed disease/PD. Objective responses for patients in the dose escalation phase will be summarized by dose cohort assigned as well as the dose at which the response occurred. Responses will be tabulated separately for expansion cohorts 1-4. For each expansion cohort, the response rate will be calculated as the number of CR or PR divided by the number of response evaluable patients. To meet the definition of response-evaluable, patients must have undergone radiographic assessment at baseline, received at least one dose of IMGN853, and must have had at least one post-dose tumor assessment.

Duration of Response (DOR) – DOR, defined as the time from initial response until progressive disease, will be estimated for all patients who achieve a confirmed objective response (PR or CR) using the method of Kaplan-Meier. Results will be summarized by dose cohort assigned as well as the dose at which the response occurred.

Progression Free Survival (PFS) – PFS, defined as the time from initiation of study drug until progressive disease or death whichever occurs first, will be estimated using the Kaplan-Meier method. Results will be summarized by dose cohort.

Time to Progression (TTP) - TTP defined as the time from initiation of study drug until progressive disease, will be estimated using the method of Kaplan-Meier. Results will be summarized by dose cohort.

For DOR, PFS, and TTP calculations, subjects not achieving the endpoint will be censored at the time of the last endpoint assessment. Median response times and associated 95% CIs will be presented for descriptive summaries.

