3.7.2. Response-Evaluable Population

To meet the definition of response-evaluable, patients must have
EITHER:

- received a radiographic assessment at baseline,
- received at least one dose of IMGN853, and

- have had at least one post-dose tumor assessment;

OR

- have died within 105 days of receiving their first dose, or
- have clinically progressed within 105 days of receiving their first dose.

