5.1.2. Objective Response Rate

The objective response rate (ORR) will be calculated as the number of subjects with a BOR of CR or PR divided by the number of subjects in the Response-Evaluable population. Subjects without at least one post-baseline RECIST assessment will be treated as non-responders. ORR with 95% confidence intervals will be reported for each group.

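### The SAP analyses PFS, TTP and OS in a Response-Evaluable set defined by post-dosing events although the protocol says all treated patients; for ORR the protocol contradicts itself, and the set used can only raise the rate

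*SAP*

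**What the plan says.** SAP section 5 sets the default: "Efficacy analyses will use data from the Response-Evaluable population unless otherwise specified". SAP Table 5 agrees. The ORR section (5.1.2) names that set as its denominator. The PFS, TTP and OS sections name no population and so inherit it. Only CA-125 response has its own set.

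SAP 3.7.2 gives two routes into the Response-Evaluable set. The first needs a baseline radiographic assessment, at least one dose, and to "have had at least one post-dose tumor assessment". The second admits patients who "have died within 105 days of receiving their first dose" or who clinically progressed within the same 105 days. SAP 5.1.2 adds: "Subjects without at least one post-baseline RECIST assessment will be treated as non-responders".

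The protocol makes two statements. Section 11 says: "All analyses will be performed for any patient that received study drug". Section 11.4 says that for each expansion cohort "the response rate will be calculated as the number of CR or PR divided by the number of response evaluable patients", and that such patients "must have had at least one post-dose tumor assessment". Section 11.4 names no subset for PFS or TTP. OS is not a listed endpoint in either document; the SAP adds it in 5.1.8.

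**The concern.** A patient's place in the efficacy analysis depends on what happened after the first dose. A treated patient who withdraws, is lost to follow-up or starts other therapy before any post-dose scan, and is not known to have died or clinically progressed by day 105, is left out of every efficacy summary except possibly CA-125 response. The same applies to a patient who stops for toxicity and has no later scan, and to one with no baseline scan. Had that patient died on day 100, the patient would be in.

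Three things are at stake:

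- **ORR.** A dropped patient cannot have a RECIST response, so the numerator is unchanged and the denominator shrinks.
- **OS.** This endpoint needs no scan, yet its population is selected partly on early death.
- **Which population applies.** A programmer cannot satisfy both protocol section 11 and SAP section 5 for PFS, TTP and OS.

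The protocol says these data will help guide further development, so the denominator should be unambiguous.

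**Working it through.** **The plan's own figure.** SAP 2.3.3.2 gives a 99.9% probability of at least one response in 40 patients at a true rate of 20%. Check: 1 − 0.80^40 = 0.99987. It reproduces, as do all 18 cells of SAP Table 4 (protocol Table 16) to within 0.001. None of these figures rests on the choice of population.

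**Who is in and who is out.**

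| Treated patient | Response-Evaluable? | ORR |
|---|---|---|
| Baseline scan and a post-dose assessment | Yes | By best response |
| No post-dose assessment, died by day 105 | Yes | Non-responder |
| No post-dose assessment, clinically progressed by day 105 | Yes | Non-responder |
| No baseline scan or no post-dose assessment, neither event by day 105 | No | Not counted |

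**ORR.** Inputs: N = 40 (planned size of Cohorts 1 and 5); x responders (illustrative); k treated patients outside the set. The documents do not give k, so 0 to 8 (0% to 20%) is an assumption. Formula: ORR = x/(40 − k), with exact (Clopper–Pearson) 95% intervals.

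| k dropped | x = 8 | x = 12 |
|---|---|---|
| 0 (all treated) | 8/40 = 20.0% (9.1–35.6) | 12/40 = 30.0% (16.6–46.5) |
| 2 | 8/38 = 21.1% (9.6–37.3) | 12/38 = 31.6% (17.5–48.7) |
| 4 | 8/36 = 22.2% (10.1–39.2) | 12/36 = 33.3% (18.6–51.0) |
| 6 | 8/34 = 23.5% (10.7–41.2) | 12/34 = 35.3% (19.7–53.5) |
| 8 | 8/32 = 25.0% (11.5–43.4) | 12/32 = 37.5% (21.1–56.3) |

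Dropping 5% to 20% therefore adds 1.1 to 5.0 points at an all-treated ORR of 20%, and 1.6 to 7.5 points at 30%.

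**PFS and TTP.** Under SAP 5.1.3 and 5.1.5, a patient with no baseline or no post-baseline scan is censored on Day 1. For PFS, death within 105 days is the exception, but a patient with that event is already in the set. Every dropped patient would therefore be censored on Day 1 if restored. The Kaplan–Meier estimate is the product of (1 − d/n) over event times. Someone censored on Day 1 has left the risk set before any later event, so no n after Day 1 changes. A check with 36 simulated event times, with and without 4 Day 1 censorings, gave the same median. Only the reported N differs.

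**OS.** Let d be the deaths by day 105. All of them are in the set, because death by day 105 is an entry route. If all patients are followed to day 105, survival there is 1 − d/N in all treated patients and 1 − d/(N − k) in the restricted set. With N = 40 and k = 4, the restricted estimate is lower by d × (1/36 − 1/40) = d/360, about 0.28 points per early death. The gap is smaller if the dropped patients were themselves censored early. After day 105 the direction depends on their later course, which the documents cannot settle.

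**DOR and TTR** are defined only in responders, so the choice of set does not affect them.

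**The case against.** The case on the other side is substantial, and much of it stands.

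- A reader might infer that the set removes early failures. It does not: deaths and clinical progressions by day 105 are kept, and those without a RECIST assessment count as non-responders. The SAP set is wider than the response-evaluable set in protocol 11.4, which has no such route.
- A reader might infer that the SAP departs from the protocol on ORR. It follows the specific rule in protocol 11.4. The ORR conflict lies between protocol sections 11 and 11.4.
- A reader might infer that PFS and TTP are biased by the restriction, or that the Day 1 censoring rule proves an all-treated set was meant. The estimates do not move. The rule is also needed for patients who enter by the second route without scans, so it proves nothing. Early clinical progressors without scans are indeed censored on Day 1 for TTP, and for PFS unless they died within 105 days. That comes from the censoring rules, not from the population.
- Most patients stopping for toxicity should be scanned. Protocol 10.7 and 10.8 call for imaging at end of treatment and at 28-day follow-up if progression is not yet documented, then every 12 weeks until progression or new therapy. The dropped group may be small.
- No hypothesis is tested, the primary endpoints are MTD and RP2D, and the illustrated ORR shift lies well inside the confidence interval. The SAP lists BOR for all patients, so an all-treated ORR could be rebuilt.

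This limits the harm without removing the point. Listings do not replace a stated denominator, the ORR error has one direction, and nothing in the documents explains why OS should be restricted.

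**Conclusion.** The point holds in a limited form. For PFS, TTP and OS, SAP section 5 conflicts with protocol section 11. For ORR, the protocol conflicts with itself and the SAP takes the narrower side.

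The numerical consequence is confined to ORR and OS. ORR can only be raised: 3.3 points with 12 responders if 4 of 40 are dropped, and 1.6 to 7.5 points across an assumed 5% to 20%. These sizes rest wholly on the assumed number dropped. OS is conditioned on early outcome without a stated reason; any bias in early OS is downward, so the restriction does not flatter early survival. For PFS and TTP the defect is the contradiction and the reported N.

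The documents do not support saying that early deaths or progressions are hidden, or that the primary endpoints are affected. The matter should be settled before database lock.

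**What to change.** - **SAP 3.7 (with Table 5) and 5:** name the Safety population for PFS, TTP and OS.
- **SAP 5.1.1, 5.1.2 and 5.2.1:** report BOR and ORR on all treated patients, counting NE as non-response. Show the Response-Evaluable ORR beside it, labelled as such.
- **Patient accounting:** for each group, state how many treated patients fall outside the Response-Evaluable set and why.
- **Protocol 11 and 11.4:** reconcile the all-treated statement with the response-evaluable denominator, so that one rule governs ORR.

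The cost is SAP wording, a protocol clarification and one extra table. No new data are needed, and SAP 1.1 allows changes until database lock. The all-treated ORR will be slightly less favourable if any patients fall outside the set.

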All new patients enrolled in the trial will receive IMGN853 at the MTD of 6 mg/kg once every three weeks (Figure 3). Safety data available to date indicate that the MTD is equal to the RP2D. Patients currently receiving IMGN853 study treatment according to Schedule B will continue to do so.

Safety and tolerability will be further defined for the patient populations evaluated in the Dose Expansion phase of the study. The dose expansion cohorts will additionally investigate IMGN853 Pd (MTD Expansion Cohort3), preliminary anti-tumor efficacy (MTD Expansion Cohorts 1, 2 and 4), and will assess the effectiveness of primary, prophylactic steroid eye drops in preventing or lessening ocular toxicity (Cohort 5).

- a. **Expansion Cohort #1** Patients with EOC, primary peritoneal cancer or fallopian tube cancer, which is resistant to their last platinum-based therapy, excluding those patients with primary platinum refractory disease.
- b. **Expansion Cohort #2** Patients with FOLR1-positive uterine cancer that is advanced or recurrent and has received at least one platinum-based regimen, and no more than five prior systemic treatment regimens for EC

ImmunoGen, Inc. Confidential Page 35 of 138

- c. **Expansion Cohort** #3 Patients with biopsy-accessible relapsed or refractory ovarian cancer, primary peritoneal cancer or fallopian tube cancer
- d. **Expansion Cohort** #4 patients with relapsed and refractory NSCLC adenocarcinoma or BAC
- e. **Expansion Cohort** #5 Patients with EOC, primary peritoneal cancer or fallopian tube cancer, which has relapsed following platinum-based therapy, excluding those patients with primary platinum refractory disease or low grade or clear cell ovarian cancer. Patients enrolled in this cohort will be pre-treated with corticosteroid eye drops to assess whether prophylaxis with topical steroids prevents or lessens severity of keratopathy and blurred vision.

Translational research studies described above and outlined in Section 7 should provide data that will help define IMGN853's mechanism of action and help guide further clinical development.

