2.4. Secondary Endpoints

- Treatment-emergent adverse events and clinically significant ≥ Grade 3 changes in laboratory test results, physical examination, ECGs or vital signs
- Treatment-emergent ocular adverse events
- PK parameters: C_{max}, AUC, terminal half-life (t_{1/2}), clearance (Cl), volume of distribution at steady state (V_{ss}), T_{max}, AUC
- Number of patients with RECIST 1.1 criteria (Appendix E) clinical responses and/or number of patients with GCIG CA-125 criteria clinical responses (Appendix F)
 - Objective response rate (ORR; MTD Expansion Cohorts # 1 and 2)
 - Duration of response (DOR)
 - Progression-free survival (PFS)
 - Time to progression (TTP)
- Human-Anti-Human Antibody (HAHA) and Human-Anti-Drug Antibody (HADA) levels

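### SAP 5's efficacy groups leave out NSCLC Cohort 4, give Cohort 1 no ORR interval of its own and drop dose from escalation; its ORR also needs a confirmation that the protocol's ORR text does not state

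*SAP*

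**What the plan says.** **Groups in the SAP.** Section 5 sets the default: "patients will be analyzed in the following groups: Escalation Schedule A, Escalation Schedule B, EOC Expansion Cohorts, Endometrial Expansion Cohort". Sections 5.1.2 and 5.2.1 to 5.2.4 then report ORR, PFS, DOR and TTP by group. Section 5.2.7 treats the EOC expansion cohorts as Cohorts 1, 3 and 5 together.

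**Groups in the protocol.** For expansion, Section 11.4 says "Responses will be tabulated separately for expansion cohorts 1-4" and "For each expansion cohort, the response rate will be calculated as the number of CR or PR" over the response-evaluable patients. For escalation, responses "will be summarized by dose cohort assigned as well as the dose at which the response occurred", and DOR gets the same treatment. For PFS and for TTP it says "Results will be summarized by dose cohort".

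**Which cohorts carry efficacy.** Protocol 1.7 assigns "preliminary anti-tumor efficacy (MTD Expansion Cohorts 1, 2 and 4"). The secondary endpoint in Protocol 2.4, repeated in SAP 2.2.2, is "Objective response rate (ORR; MTD Expansion Cohorts # 1 and 2").

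**Confirmation.** SAP 5.1.1 asks for a repeat assessment at least 28 days after a CR or PR is first met, and SAP 5.1.2 counts ORR from that BOR. Protocol 11.4's ORR text has no such condition, and Appendix E takes BOR as the best response at any time point. Protocol 11.4 uses the word confirmed only for DOR, which "will be estimated for all patients who achieve a confirmed objective response (PR or CR) using the method of Kaplan-Meier".

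**The concern.** The protocol leaves the full description of the analyses to the SAP, so a programmer who follows SAP 5 will produce tables that differ from Protocol 11.4, and the SAP gives no reason for the change. Four things are at stake:

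- A cohort named for efficacy has response percentages but no interval and no PFS, DOR or TTP summary.
- A named secondary endpoint, the Cohort 1 ORR, has no interval of its own. The three EOC cohorts differ by eligibility: Cohort 1 needs platinum resistance, measurable disease and at most five prior regimens; Cohort 3 has no limit on prior regimens; Cohort 5 needs three or four. Cohorts 3 and 5 both accept non-measurable disease.
- Escalation outcomes lose the dose breakdown that the protocol states.
- Confirmed and unconfirmed ORR are different quantities, so the protocol's reader may expect a different ORR from the one the SAP yields.

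**Working it through.** **1. The plan's own response figure.** SAP 2.3.3.2 and Protocol 11.1 give a 99.9% chance of at least one response in each 40-patient cohort at a true rate of 20%. The check is 1 − 0.8^40 = 0.99987, so it reproduces. The figure is stated per cohort, not for a pool.

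**2. Coverage of the four groups** (planned sizes, Protocol 4.1.1 and SAP 2.3.3.2).

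- Total: 44 + 25 + 40 + 20 + 20 + 20 + 40 = 209, as stated.
- Expansion: 40 + 20 + 20 + 20 + 40 = 140.
- Without Cohort 4: 209 − 20 = 189 overall and 140 − 20 = 120 in expansion.
- EOC pool: 40 + 20 + 40 = 100, of which Cohort 1 is 40.

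**3. What each set of patients gets under the SAP text.**

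| Set | Response counts and percent | ORR with CI | PFS, DOR, TTP |
|---|---|---|---|
| Cohort 4 | yes (5.1.1 with 3.8) | no | no |
| Cohort 1 alone | yes (5.1.1 with 3.8) | no, if the EOC group is a pool | no, if the EOC group is a pool |
| Cohort 2 | yes | yes | yes |
| Escalation, by dose | listing only | by schedule | by schedule |

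SAP 3.8 would otherwise summarize by dose cohort or treatment group, but it gives way to later sections, and Section 5 sets the schedule groups. Time to response is less settled: SAP 5.1.6 summarizes it for each expansion cohort, SAP 5.2.5 by group.

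**4. What pooling can do to Cohort 1** (illustrative; rates taken from the columns of the plan's own probability table). Pooled ORR = 0.4 × p1 + 0.6 × p35, where p1 is the Cohort 1 rate and p35 the rate in Cohorts 3 and 5 together. With p1 = 20%:

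- p35 = 10%: 8 + 6 = 14%
- p35 = 20%: 8 + 12 = 20%
- p35 = 30%: 8 + 18 = 26%

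The pool could read 6 points low, equal, or 6 points high.

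**5. What an interval adds for Cohort 4.** With 0 of 20 responses, the exact 95% upper limit is 1 − 0.025^(1/20) = 16.8%. A bare 0% does not show that.

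**6. Confirmation** (illustrative; the unconfirmed number is an assumption). Take 12 first responses in 40, which is 30%. If 1 is not confirmed, 11/40 = 27.5%. If 4 are not confirmed, 8/40 = 20%.

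**7. Escalation by dose.** SAP Table 2 plans eight Schedule A levels, from 0.15 to 9.0 mg/kg: four with one patient and four with at most six. That is at most 4 + 24 = 28 of the 44 planned patients. The table does not place the other 16; intermediate doses were allowed, and the weight basis for dosing changed at Amendment 5. By-dose results are therefore small counts.

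**The case against.** The strongest reply is that the per-cohort response rate is largely there. SAP 5.1.1 summarizes BOR for each expansion cohort and SAP 3.8 gives number and percent, so adding the CR and PR percentages gives a response percentage for Cohort 4 and for Cohort 1. That stands. A reader might infer that Cohort 4 has no efficacy output, or that the SAP abandons per-cohort responses; the documents support neither.

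It also stands that Protocol 11.4 promises no confidence interval for ORR and no PFS or DOR by expansion cohort, and that the named ORR endpoint covers Cohorts 1 and 2 only. Adding those items for Cohort 4 improves the plan; their absence is not a departure from the protocol.

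Pooling is an inference. SAP 5 uses a plural and never says combined, and the table shells are a separate document not available here. Still, SAP 5.2.7 handles the three cohorts as one set, and its platinum-resistant subgroups draw on all three, so none isolates Cohort 1.

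On confirmation, a reader might infer a flat contradiction on every response outcome. The protocol is itself mixed, since its DOR text says confirmed. Appendix E also marks CR and PR with asterisks whose note is not in the available text. SAP 5.1.1 does not say how an unconfirmed PR is classified. The mismatch is confined to ORR and needs reconciling.

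Finally, a reader might take 44 minus the four single-patient levels to mean that 40 patients support response rates by dose. SAP Table 2 does not show that, and BOR listings keep individual responses recoverable. The protocol nevertheless states a by-dose summary, and the SAP text does not plan one.

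**Conclusion.** The point holds in a limited form. Two parts are mismatches with the protocol's text: escalation summaries by dose, and a confirmation condition on ORR. Two are gaps in the SAP's own coverage: Cohort 4 (20 of 140 planned expansion patients) has no group, and Cohort 1 (40 of the 100 in the pool) has no ORR interval of its own. The Cohort 1 part rests on reading the EOC group as a pool.

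The numerical effect is unknown. The 14% to 26% and 20% to 30% ranges rest on assumed rates and assumed unconfirmed responses, and the coverage figures are planned numbers. The study has no formal hypothesis test, its primary endpoints are MTD and RP2D, and efficacy is secondary and descriptive. Severity is minor to should-fix.

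**What to change.** In SAP 5:

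- Report ORR with an exact 95% CI for each expansion cohort, including Cohort 4.
- Add Cohort 4 as a group for PFS, DOR and TTP.
- Keep the EOC pool as a supplementary group, and state that it is Cohorts 1, 3 and 5 combined.
- Restore Protocol 11.4's by-dose escalation summaries (assigned dose and dose at response for responses and DOR; dose cohort for PFS and TTP) as descriptive counts.

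In SAP 5.2.1, delete medians, which do not apply to a response rate, and name the interval method. State one confirmation rule for ORR in both documents and show the other version as a sensitivity line.

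This needs wording and table columns, no new data. The cost is wider intervals. At an observed 20%, the exact (Clopper-Pearson) 95% limits are:

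- 8/40: 9.1% to 35.6%
- 4/20: 5.7% to 43.7%
- 20/100, the pool: 12.7% to 29.2%
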